## 2. Experimental Protocol

The study will be carried out on the beaches of Areia Preta de Guarapari (source of monazitic sands) and on the beach of Itapoã in Vila Velha (sand without radiation). Selected patients will have their knees fully covered with beach sand, properly analyzed for radioactivity and temperature, for 30 minutes on 2 mornings a week for a period of 1 (one) year.

Patients will be enrolled in relation to age, gender, weight, height and body mass index (BMI). An investigation / monitoring will be performed regarding the current use of medications for disease control and associated comorbidities.

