# 3. The size of the sample

The sample size of the patients was calculated considering the necessary amount of subjects to detect difference of at least 3 points in the pain perception through the visual analgesic scale (scale from 0 to 10), considering a significance level of 1% and test power of 95% in two-tailed hypothesis test, as well as the value of 4 for standard deviation (MATA et al., 2015). The sample was calculated in 126 patients and considering a sample loss around 20%, the number of subjects was 150, with 75 subjects in each sample (BENAZZI, FIGUEIREDO, BANASSI, 2010).

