## 7. Removal criteria

Patients will be removed when:

- Undergoing knee surgery during the course of the research.
- Subjected to joint infiltration with corticoids or any other type and medication of intraarticular use.
- Heat intolerant or other discomfort during exposure to sand.

For evaluation and follow-up of the volunteers will be carried out in parallel a work of pharmaceutical attention with monitoring of the use and frequency of medications, especially the use of analgesics and / or anti-inflammatories.

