#### 9. Intervention

Patients selected for the study will have their knee (s) affected by OA fully submerged in the beach sand 2 (two) times per week for 30 (thirty) minutes each session at the same location and at the same time of day.

The natural gamma (②) radiation doses of the monazite sands will be monitored in both groups through equipment that counts and accumulates the records for the desired time. In addition, the radiation measurements ② will be associated with the atmospheric and climatic measurements of each group. An interview with the patients will be performed initially (Appendix B), blood collected for analysis and applied to the Visual Analogue Scale (Annex C) and WOMAC (Annex D). The questionnaires as well as the blood collection for laboratory analysis will be repeated at the beginning of the study (day zero) and after 1, 2, 3, 6, 9 and 12 months for later analysis and comparison of the data.

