### 10.2 Secondary Outcome Measures:

- Change total score (0 96) the Western Ontario and McMaster Universities
  Osteoarthritis Index (WOMAC)- (lower scores indicate lower levels of symptoms or physical disability)
- Reduction of Nonspecific inflammatory markers: evaluation of nonspecific inflammatory markers (HSV and CRP) and specific (IL-1β, IL-6, IL-8, IL-17, TNF-α and TGF-β)
- Reduction of Self-medication to treat pain

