#### 13.3 Pharmaceutical Care

It consists of evaluating the patients' pharmacological therapy, being able to collect data on the health situation, use of medications and dosages administered, as well as adverse reactions and possible drug interactions.

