## 14. Statistical analysis

Statistical analysis will be performed in the SPSS program (Statistical Package for the Social Sciences, version 13.0). For the analysis, descriptive statistics will be performed, with measures of central tendency (mean, median and standard deviation), for variables that follow the normal distribution. Qualitative variables will be expressed in frequency and percentage. The difference will be analyzed by the chi-square test or Fischer test for the categorical variables and the Mann-Whitney and Student tests for the resulting variables. A statistically significant difference will be considered when p <0.05.

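### Every listed outcome measures benefit; the plan does not require removals for sand intolerance to be reported by arm, and it specifies no scheduled question on reactions after a session

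*Combined protocol and SAP*

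**What the plan says.** All references are to the combined protocol and SAP.

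- **Outcomes.** Section 10.1 names change in VAS pain. Section 10.2 adds the WOMAC total, a reduction in inflammatory markers ("evaluation of nonspecific inflammatory markers (HSV and CRP) and specific" cytokines) and a reduction in self-medication for pain. None measures tolerance or harm.
- **Removal.** Section 7 removes patients for knee surgery, for joint infiltration, or when "Heat intolerant or other discomfort during exposure to sand". One rule covers both arms. It does not ask for removals to be tabulated by arm with reasons.
- **Parallel follow-up.** Section 7 also sets up pharmaceutical care for all volunteers, with "monitoring of the use and frequency of medications, especially the use of analgesics and / or anti-inflammatories". Section 13.3 describes it as an evaluation of drug therapy that can collect data on health and medicines, "as well as adverse reactions and possible drug interactions".
- **Alarm signals.** Section 13 has the questionnaire staff trained in potential alarm signals. It does not define the signals or say how they are recorded.
- **Schedule.** Under section 9, questionnaires and blood collection "will be repeated at the beginning of the study (day zero) and after 1, 2, 3, 6, 9 and 12 months".
- **Blood timing.** Section 11 places the blood draws, time zero included, directly after the patient has been exposed to sand.
- **Analysis.** Section 14 states that "The difference will be analyzed by the chi-square test or Fischer test for the categorical variables". It names no variables, so it names no harm or removal summary.
- **Size.** Section 3 says that "considering a sample loss around 20%, the number of subjects was 150, with 75 subjects in each sample".

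**The concern.** Patients aged 30 to 95 are to have their knees covered with sand twice a week for a year. The plan foresees that some will not tolerate this, because it has a removal rule for it. A reader of the results will want to set any pain benefit against the number in each arm who could not continue or who reacted to the sand.

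Two kinds of information are at risk. Removals for intolerance may be reported only as part of overall sample loss. That can be repaired later if the reasons are kept. Reactions that appear after a session fall outside the removal rule, which covers only the time of exposure. If nobody asks about them in a set way, they cannot be reconstructed afterwards.

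The blood timing is a separate, smaller matter. If the baseline sample follows a session, the baseline for the inflammatory markers is not an untreated one.

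**Working it through.** **1. The plan's own figure.** Section 3 gives a difference of 3, SD of 4, two-sided alpha of 0.01 and power of 0.95. The normal approximation is n per arm = 2 × SD² × (2.576 + 1.645)² / 3² = 2 × 16 × 17.81 / 9 = 63.3. Rounded up, that is 64 per arm or 128 in total, against 126 stated. The figure reproduces to within 2 patients and has no bearing on this point beyond fixing the loss allowance.

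**2. Loss allowance.** 150 − 126 = 24 patients, which is 24/150 = 16% of those enrolled or 24/126 = 19% of those needed.

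**3. Exposure.** 2 × 52 = 104 sessions per patient. The 3-month gap between late visits covers 104/4 = 26 sessions.

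**4. What each section would capture.**

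| Event | Where it could be caught | What is not specified |
|---|---|---|
| Intolerance or discomfort during a session | Section 7 removal | Reporting by arm with reason |
| Skin reaction or discomfort after a session | Possibly section 13.3 or the section 13 alarm signals | A scheduled question, a definition, a recording rule, a by-arm summary |

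**5. How differently 24 losses could be divided.** The documents give no event rate, so the splits below are assumptions. Each supposes that all 24 losses are intolerance removals. That is an upper limit, because knee surgery, infiltration and ordinary dropout draw on the same allowance. The denominator is 75 per arm and the test is the two-sided Fisher exact test.

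| Split | Percentages | p |
|---|---|---|
| 18 vs 6 | 24.0% vs 8.0% | 0.013 |
| 16 vs 8 | 21.3% vs 10.7% | 0.12 |
| 15 vs 9 | 20.0% vs 12.0% | 0.27 |
| 12 vs 12 | 16.0% vs 16.0% | 1.0 |

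The p-values only show how far apart these situations are. They are not a proposed test.

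**6. Precision with 75 per arm.** With no events, the one-sided 95% upper bound is 1 − 0.05^(1/75) = 3.9%. The upper limit of the exact two-sided 95% interval is 1 − 0.025^(1/75) = 4.8%. With 4 of 75 (5.3%), the exact 95% interval is 1.5% to 13.1%. Exact Fisher power at 0.05 is 9% for an assumed 1% vs 5%, 44% for 5% vs 15% and 76% for 5% vs 20%. A descriptive summary is therefore the right level.

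**7. Day-zero blood.** Section 11 lists time zero among draws taken directly after exposure. Section 9 speaks of blood collected initially and then repeated on day zero and later, which may mean an earlier, pre-exposure draw. The two sections do not settle the order.

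**The case against.** The strongest reply is that the plan has more safety content than a list of outcomes suggests, and much of that stands.

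- A reader might infer that the plan gives no count of intolerance by arm. It does not go that far: section 7 applies one removal rule to everyone, so removals during exposure can be counted by arm once allocation is known. What is missing is the requirement to report them with reasons.
- A reader might infer that no adverse-reaction data are collected. Section 13.3 does collect adverse reactions, and section 7 places that work within follow-up of all volunteers. It is framed as a review of drug therapy, but it can be read as reaching some sand reactions. The supportable wording is that a question about the sand is not specified, not that patients are never asked. The alarm signals in section 13 add something, though undefined. Appendix B, the initial interview, is not in the available text and cannot be checked.
- Sections 2 and 9 measure the sand's radioactivity and temperature and monitor dose, and section 6 excludes a history of skin cancer. These are sensible precautions, but they describe exposure and eligibility, not harm.
- The two sands lie on different beaches, so a reader might infer that discomfort would be noted differently by arm. No section says so. An identical question standardises the wording but would not separate beach from arm.
- The 18 vs 6 split alone would be a selective illustration, which is why the range is shown.
- Discomfort during exposure already triggers removal, so that part of the question largely repeats the removal record. The new information is what happens after sessions, recalled over up to three months.

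**Conclusion.** The point holds in limited form. All listed outcomes are efficacy measures, the plan does not require section 7 removals to be reported by arm with reasons, and it specifies no scheduled question on reactions after a session. The first gap can be closed at reporting if reasons are kept. The second has to be closed before data collection.

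The size of any harm is unknown. The documents give no rates, and the splits of 24 losses are assumptions that also take every loss as intolerance. The documents do not support a claim that one arm tolerates the sand worse, that harm is being ignored altogether, or that the primary analysis is affected. The reading rests on the outcome, follow-up and analysis sections only. This should be changed, with medium confidence.

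The blood timing is a minor and separate point: on a literal reading of section 11 the baseline follows exposure, while section 9 leaves room for an earlier draw.

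**What to change.** **Section 10.2.** Add one descriptive tolerability outcome: the number and percentage of all randomised patients per arm (75) with any section 7 removal, or any skin reaction or discomfort during or after a session, with exact 95% confidence intervals. Show removals by reason, so that surgery and infiltration are not read as intolerance.

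**Collection.** Ask one identical yes/no question in both arms at months 1, 2, 3, 6, 9 and 12 and at removal.

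**Section 14.** Add the corresponding by-arm table, labelled descriptive, with no hypothesis test.

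**Section 11.** State that the day-zero sample is drawn before the first sand exposure, so that the biomarker baseline is untreated.

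**Cost.** One outcome entry, one table and at most 150 × 6 = 900 visit answers, plus one at each removal. No extra patients, visits or laboratory tests are needed, although day-zero blood may have to be drawn at a different time that day. The drawbacks are recall over as much as 3 months (about 26 sessions) and low precision, since an arm with no events would still be compatible with a rate of up to 3.9%.

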#### 8. Recruitment of volunteers

The volunteers will be recruited at the basic health units of the municipality of Vila Velha for internal dissemination and with the assistance of the Community Teaching Service Interaction Program (PISEC) of the Medicine Course of the Vila Velha University to disseminate the project to pre-formed groups example: HIPERDIA or group of elderly).

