#### 5. Inclusion criteria

Will be included in the study:

- Patients who meet the NICE (2014) diagnostic criteria for Primary Knee Osteoarthritis.
- Age between 30 and 95 years.

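### Recruitment is confined to Vila Velha, where the control beach is, and nobody has to be able to attend the Guarapari beach before randomisation, so refusal and loss may depend on the allocated arm; direction and size are unknown.

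*Combined protocol and SAP*

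**What the plan says.** All references are to the combined protocol and SAP.

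- **Recruitment (section 8).** "The volunteers will be recruited at the basic health units of the municipality of Vila Velha", with help from the "Community Teaching Service Interaction Program (PISEC) of the Medicine Course of the Vila Velha University". No route in Guarapari is named.
- **Sites (section 2).** The study takes place "on the beaches of Areia Preta de Guarapari (source of monazitic sands) and on the beach of Itapoã in Vila Velha (sand without radiation".
- **Attendance (sections 2 and 9).** The knees are covered with sand "for 30 minutes on 2 mornings a week for a period of 1 (one) year", and section 9 holds "each session at the same location and at the same time of day".
- **Eligibility (sections 5 and 6).** Inclusion requires the NICE diagnosis of primary knee osteoarthritis and "Age between 30 and 95 years". The exclusions are clinical. Neither list mentions the ability or willingness to attend a given beach.
- **Loss (section 3).** One overall figure of around 20% is planned, with 75 subjects in each sample and no split by arm.
- **Outcome and analysis (sections 10.1 and 14).** The primary outcome is change in VAS pain. The tests are two-group comparisons at 5%. No analysis population or missing-data method is stated.

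**The concern.** Randomisation makes the arms comparable at the moment of allocation. Here the next step differs by arm: a patient allocated to control stays in the municipality of recruitment, while a patient allocated to monazite goes to another town for each session. The population has painful knees and may be as old as 95, so some volunteers may be unable to keep that up, or may decline once they know which beach is theirs.

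Since the eligibility criteria do not screen for this, such patients can be randomised. If they then refuse or stop coming more often in one arm, the patients left in the two arms may no longer be comparable. At stake is the validity of the primary VAS comparison. A larger sample would not remove a bias of this kind.

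**Working it through.** **1. Inputs from the documents.** Difference 3 points, SD 4, two-sided 1%, power 95%, 126 patients before loss, about 20% loss, 150 randomised as 75 per arm (section 3); analysis at 5% (section 14); two sessions a week for one year (section 2).

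**2. The plan's own figure.** n per arm = 2 × (SD/difference)² × (z₀.₉₉₅ + z₀.₉₅)² = 2 × (4/3)² × (2.576 + 1.645)² ≈ 63.3, which rounds up to 64 per arm, or 128 in all. The stated 126 (63 per arm, power 0.949) agrees within rounding. This point does not dispute the sample size.

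**3. Burden.** 2 × 52 = 104 sessions. For volunteers from Vila Velha, all of them are in the home municipality in one arm and in Guarapari in the other.

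**4. Inputs that are assumed.** The documents give neither loss by arm nor the outcome of patients lost. Take losses L_m (monazite) and L_c (control). Let D be the number of VAS points by which the mean change of patients lost is worse than that of patients retained, the same in both arms.

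**5. Bias formula.** The mean of all randomised patients in an arm equals the completers' mean plus L × (mean of those lost − mean of completers). A completers-only arm therefore looks better by L × D, and the comparison is biased by (L_m − L_c) × D.

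- L_m = 30%, L_c = 10%, D = 2: 0.30 × 2 − 0.10 × 2 = 0.6 − 0.2 = 0.4 points.
- Same losses, D = 0 (loss unrelated to pain change): 0.
- Same losses, D = −2 (patients lost would have improved more): −0.4, the opposite direction.
- Equal losses of 20% and any common D: 0.

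**6. Error rate when there is no true effect.** With 60 per arm (75 × 0.80) and SD 4, SE = 4 × √(1/60 + 1/60) = 0.730. The standardised bias is 0.4/0.730 = 0.548. Two-sided rejection at 5% is Φ(−1.960 + 0.548) + Φ(−1.960 − 0.548) = 0.079 + 0.006 = 0.085; the noncentral t gives 0.084. With the unequal numbers that 30% and 10% loss imply (about 52 and 68), the normal formula also gives 0.084.

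**7. Range over the assumptions** (SD 4, normal formula, nominal 5%):

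| Loss, monazite / control | Size of D | Bias (points) | Error rate |
|---|---|---|---|
| 30% / 10% | 1 | 0.2 | 5.8% |
| 30% / 10% | 2 | 0.4 | 8.4% |
| 30% / 10% | 3 | 0.6 | 12.9% |
| 40% / 10% | 1 | 0.3 | 6.8% |
| 40% / 10% | 2 | 0.6 | 12.2% |
| 40% / 10% | 3 | 0.9 | 21.6% |

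The test is two-sided, so the error rates are the same whichever way the bias points.

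**8. Power.** For a true 3-point difference at two-sided 1%, noncentral t power is 0.930 with 60/60, 0.925 with 52/68 and 0.898 with 45/68 (40% and 10% loss). Imbalance alone costs little; the issue is bias.

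**The case against.** The strongest objection is to the direction. A reader might infer that monazite completers would be the more mobile patients with less pain, and that the bias therefore favours monazite. That does not follow. The primary outcome is change in VAS on a 0 to 10 scale, and patients who start with less pain have less room to improve, so retaining them could work against monazite. Loss caused by distance, transport or work may have nothing to do with pain change. This objection stands.

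A reader might also infer that patients who cannot travel will leave the monazite arm only. That is too strong. Controls also attend two mornings a week for a year, and some of them will be lost too.

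Nor can the plan be faulted for saying nothing about transport or reimbursement. The consent pages were removed from the text under review and may cover it. Organised transport would lower the cost of the journey, though not the time it takes.

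The losses by arm and the 2-point gap in the illustration are assumptions, and 0.4 points is small beside the planned 3-point difference. Both remarks are fair and limit the weight of the point.

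Two further objections carry less. Section 1 speaks of paired samples, and if every patient attended both beaches the point would lapse. However, section 3 has 75 subjects in each sample, and section 9 refers to both groups and a fixed location, so two parallel arms is the better reading. The other objection is that asking candidates to accept either beach weakens the blinding. Patients see which beach they attend in any case, so little is given away.

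Finally, monazite sand is tied to its beach, and recruiting both arms from one municipality gives them a common source population. That is a reason to leave the recruitment area alone and check attendance before allocation.

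**Conclusion.** The point holds as a risk built into the design. The site facts are explicit: the recruitment routes are in Vila Velha, the control beach is there and the monazite beach is not, each patient keeps one location, and no criterion requires the ability to attend either one. That refusal and loss are more likely among patients allocated to Guarapari is a reasonable inference from these facts; the documents do not demonstrate it.

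The size and sign of any bias cannot be established from the documents. The illustrative 0.4 points and 8% error rate rest on three assumptions: a 20-percentage-point difference in loss, a 2-point gap in VAS change between patients lost and retained, and an analysis of completers only. The reason to act is that the remedy is cheap. The documents do not show that the comparison would be invalid.

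**What to change.** Add to section 5 an inclusion line such as: *able and willing to attend either beach two mornings a week for 12 months, whichever is allocated*. Have it confirmed and recorded at screening, before the allocation is revealed. State that refusals and losses after randomisation will be reported by arm, with reasons.

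The cost is one criterion, one screening question and a table of losses. Some volunteers become ineligible and recruitment is a little slower. The change should reduce refusal and early loss that depend on the arm. It will not prevent later loss over the 12 months, and reporting by arm with reasons is what makes that visible.

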#### 9. Intervention

Patients selected for the study will have their knee (s) affected by OA fully submerged in the beach sand 2 (two) times per week for 30 (thirty) minutes each session at the same location and at the same time of day.

The natural gamma (②) radiation doses of the monazite sands will be monitored in both groups through equipment that counts and accumulates the records for the desired time. In addition, the radiation measurements ② will be associated with the atmospheric and climatic measurements of each group. An interview with the patients will be performed initially (Appendix B), blood collected for analysis and applied to the Visual Analogue Scale (Annex C) and WOMAC (Annex D). The questionnaires as well as the blood collection for laboratory analysis will be repeated at the beginning of the study (day zero) and after 1, 2, 3, 6, 9 and 12 months for later analysis and comparison of the data.

#### 10. Values evaluated

# 10.1 Primary outcome Measure:

Change pain perception through the visual analgesic scale of the volunteers (VAS)

### 10.2 Secondary Outcome Measures:

- Change total score (0 96) the Western Ontario and McMaster Universities
  Osteoarthritis Index (WOMAC)- (lower scores indicate lower levels of symptoms or physical disability)
- Reduction of Nonspecific inflammatory markers: evaluation of nonspecific inflammatory markers (HSV and CRP) and specific (IL-1β, IL-6, IL-8, IL-17, TNF-α and TGF-β)
- Reduction of Self-medication to treat pain

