## 11. Collection of biological material

Volunteers blood samples will be taken at time zero, after 1, 2, 3, 6, 9 and 12 months, after agreement and signature of the ICF. Blood collection will be performed by a specialist in the laboratory of clinical analyzes at predetermined dates immediately after exposure of the patients to the sand. The samples will be transported in an isothermal box with ice to the Vila Velha University laboratory, where they will be immediately frozen at -80°C until analysis.

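### Ten secondary variables, six follow-up visits and one p<0.05 rule, with no analysis visit, hierarchy, correction or exploratory label: about a 29–40% chance of a false significant result even at a single visit

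*Combined protocol and SAP*

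**What the plan says.** All of the following is in the combined protocol and SAP.

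- **Section 10.2** gives the secondary outcomes: "Change total score (0 96) the Western Ontario and McMaster Universities" index; markers, introduced as "Reduction of Nonspecific inflammatory markers" and listed as "evaluation of nonspecific inflammatory markers (HSV and CRP) and specific (IL-1β, IL-6, IL-8, IL-17, TNF-α and TGF-β"; and "Reduction of Self-medication to treat pain". HSV is evidently the erythrocyte sedimentation rate of section 12.1. The count is 1 + 2 + 6 + 1 = 10 variables, 8 of them blood markers.
- **Section 9** schedules the questionnaires and blood collection at "day zero) and after 1, 2, 3, 6, 9 and 12 months for later analysis and comparison of the data". **Section 11** repeats this for blood: "Volunteers blood samples will be taken at time zero, after 1, 2, 3, 6, 9 and 12 months". That is a baseline and six follow-up visits.
- **Section 14** is the whole analysis plan. It names chi-square or Fisher tests for categorical variables and Mann-Whitney and Student tests for the others, and it ends with one threshold: "A statistically significant difference will be considered when p <0.05".

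No section names the visit at which a secondary outcome is analysed, ranks the outcomes, adjusts for their number, calls any of them exploratory, or makes a secondary claim depend on the VAS result. No repeated-measures model combines the six visits into one test.

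**The concern.** A 0.05 threshold limits the false-positive risk of one test. Here it is the only criterion for ten variables, and the reader is not told which of six visits counts. An author who follows the plan to the letter could report a significant result for any one marker, at whichever visit shows it, as evidence that monazite sand reduces inflammation, even with no difference on VAS. Nothing in the plan would identify that result as one of many looks.

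At stake is the credibility of the secondary claims. The level used for VAS is a separate matter and is not part of this point.

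**Working it through.** **The plan's own figure.** The documents give no error rate for the secondary outcomes, so there is none to reproduce. The one calculation they contain, the VAS sample size in section 3, reproduces closely: 4 × [4 × (2.576 + 1.645) / 3]² = 126.7, against the stated 126. It does not address the secondary outcomes.

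**Inputs from the documents.** 10 secondary variables, 8 of them markers (section 10.2); 6 follow-up visits (sections 9 and 11); 0.05 per test (section 14).

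**Assumptions.**
- No true effect on any secondary outcome.
- Two-sided tests, so 0.025 falls in the direction of a reduction. Section 14 does not state sidedness; section 3 is two-tailed.
- Equal correlation between outcomes of 0 to 0.5, and between visits of 0.5 to 0.8. The documents give no correlations.
- Self-medication is counted at all six visits. Sections 7 and 13.3 describe its monitoring without dates.

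**Step 1: one visit, independent outcomes.** P(at least one) = 1 − (1 − a)^k.
- Ten variables, either direction: 1 − 0.95^10 = 40.1%.
- Eight markers, either direction: 1 − 0.95^8 = 33.7%.
- Eight markers, reduction only: 1 − 0.975^8 = 18.3%.

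**Step 2: one visit, outcome correlation ρ = 0.5.** With one shared normal factor u, the either-direction probability is 1 − ∫ φ(u) [Φ((1.96 − √ρ·u)/√(1−ρ)) − Φ((−1.96 − √ρ·u)/√(1−ρ))]^k du. Dropping the second Φ gives the one-direction version.
- Ten variables, either direction: 28.7%.
- Eight markers, either direction: 25.0%.
- Eight markers, reduction only: 12.5%.

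**Step 3: all six visits, if each is tested.** That is 10 × 6 = 60 tests, with 60 × 0.05 = 3 false positives expected. Under full independence the chance of at least one is 1 − 0.95^60 = 95.4%, but repeated measurements on the same patients are correlated. Simulating null normal statistics (100,000 runs per row) gives:

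| Correlation between outcomes | Correlation between visits | Ten variables, either direction | Eight markers, either direction | Eight markers, reduction |
|---|---|---|---|---|
| 0 | 0.5 | 90.4% | 84.2% | 58.2% |
| 0 | 0.8 | 77.5% | 70.0% | 43.9% |
| 0.2 | 0.5 | 88.4% | 82.4% | 51.1% |
| 0.3 | 0.5 | 86.2% | 80.2% | 47.4% |
| 0.3 | 0.8 | 71.5% | 64.2% | 34.7% |
| 0.5 | 0.5 | 78.4% | 72.9% | 39.9% |
| 0.5 | 0.8 | 62.2% | 56.2% | 28.7% |

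**Step 4: sensitivity to the count.** Without self-medication there are 9 variables: 1 − 0.95^9 = 37.0% at one visit, and 9 × 6 = 54 tests over six visits, with 2.7 false positives expected. The picture is unchanged.

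**The case against.** **VAS is the single primary outcome and the rest are labelled secondary.** Many trials leave secondary outcomes uncorrected and read them as supportive, and the plan nowhere says that one positive marker would establish an anti-inflammatory effect. This stands in part. It is a reason not to insist on full gatekeeping, and an exploratory label would meet most of the concern. But the plan gives no such label, and it applies the same significance rule to every difference.

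**The plan does not say that each variable is tested at each visit.** This stands. Sections 9 and 11 are a collection schedule that looks ahead to later comparison. The six-visit figures are therefore conditional on testing every visit; the single-visit figures are not. The silence is itself part of the problem, because it leaves the choice of visit open until the data are seen.

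**A reader might infer that a false reduction in some marker is more likely than not.** The documents do not support that. The 62–90% counts significant results in either direction and includes WOMAC and self-medication. A reduction in a marker involves eight variables and one tail. At one visit its chance is at most 18.3%. Over six visits, in the scenarios shown, it passes one half only when the correlation between markers is 0.2 or less and that between visits is 0.5.

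**Conclusion.** The point holds as a gap in the control of secondary claims, and repairing it is a cheap improvement. Under no true effect:

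- **Any false significant result among the ten variables, either direction:** about 29–40% at one visit; 62–90% if all six visits are tested.
- **A false reduction in at least one of the eight markers:** about 12–18% at one visit; 29–58% over six visits.

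The counts, the visits, the threshold and the absence of any control come directly from the documents. The ranges rest on the assumed correlations and on two-sided testing. If section 14 meant one-sided tests at 0.05, the single-visit chance of a false marker reduction under independence would be 1 − 0.95^8 = 33.7% instead of 18.3%. The mildest reading for the full set of ten, one visit with correlation 0.5, is still nearly six times the nominal 5% (28.7 / 5 = 5.7).

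**What to change.** In section 14:

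1. Name one analysis visit for the secondary outcomes, the same as for VAS. Section 10.1 names none for VAS either, so one sentence can settle both.
2. At that visit, either apply Holm's correction across the secondary outcomes, or report them as exploratory with estimates and confidence intervals and no claim of significance.
3. Present the other visits descriptively.

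In section 10.2, word the marker outcomes as two-sided change rather than reduction.

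Testing WOMAC total first, and only if VAS succeeds, is optional. It cannot be applied until the VAS visit and significance level are settled: section 3 uses 1% and section 14 uses 0.05.

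**Cost.** A short paragraph, with no added patients, visits or assays. The downside is fewer or weaker marker claims. With ten outcomes, Holm's first step requires p ≤ 0.05/10 = 0.005. With 126/2 = 63 evaluable patients per arm and an assumed 80% power, the detectable standardised difference rises from (1.960 + 0.842) × √(2/63) = 0.50 to (2.807 + 0.842) × √(2/63) = 0.65 at that step. If that is too high a price, the exploratory route avoids it.
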